8.2 Procedures for intervention on the day of the prostate cancer consult

8.2.1 Patient arrival

Following the completion of the consent and registration procedures, the study coordinator will greet and engage participant and escort them to a private area preferably near the waiting area.

8.2.2 Arms A and B only: Patient interaction with the pre-consultation decision aid

The study coordinator will lead the participant to a designated computer terminal or will provide a tablet with which the participant, in collaboration with a partner, if desired, may interact with the pre-consultation decision aid. Staff will be available for any technical issues that may arise.

8.2.3 Physician notification

The physician or appropriate clinical staff (e.g., physician assistant) will be notified when a participant has arrived and, if at an institution randomized to Arm A or B, that the patient has spent time with pre-consultation decision aid. The physician will thereby know to follow the study protocol.

8.2.4 Consultation

Arm A: The physician or appropriate clinical staff (e.g., physician assistant) will incorporate the during-consultation decision aid in his/her conversation with the patient about treatment choice. In addition, the physician or appropriate clinical staff will engage the patient regarding any questions by the patient about the pre-consultation decision aid. Site staff will record the time that the patient spends with the pre-consultation decision aid.

Arm B: Usual care, and the physician or appropriate clinical staff will engage the patient regarding any questions by the patient regarding the pre-consultation decision aid. Site staff will record the time that the patient spends with the pre-consultation decision aid.

Arm C: The physician or appropriate clinical staff will incorporate the during-consultation decision aid into his/her conversation with the patient about treatment choice.

Arm D: Usual care.

All Arms: At the end of the consultation, the physician will remind the patient that the study coordinator has post-visit (baseline) questionnaires for the patient to complete. The study coordinator will also assess the time for the consultation, which will be recorded in a separate field on the data collection forms. This will be defined as the time from when the physician enters the consultation room to when physician's consultative activities end (i.e., when the physician leaves the room OR when the patient is handed off to the CRA to complete post-consultation forms).

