2.2 Secondary objectives

- 2.2.1** To test the impact of in-visit DA's alone compared to usual care on quality of life outcomes and treatment utilization.
- 2.2.2** To test the impact of out-of-visit DA's alone compared to usual care on quality of life outcomes and treatment utilization.
- 2.2.3** To test the impact of combined in-visit and out-of-visit DA's compared to both usual care and individual DAs on quality of life outcomes and treatment utilization.
- 2.2.4** To test the comparative effectiveness of DA's on minority men's knowledge.
- 2.2.5** To compare clinic time required to administer the DA's across arms.

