7.2 Site training

Before enrolling patients, each site randomized to one of three intervention arms must determine their desired mode of delivery for the decision aids (either by desktop computer or tablet). Sites that opt for tablet delivery of the decision aid will receive a tablet from the investigative team: Either by shipment or by hand delivery, depending on whether or not a member of the study team travels to the participating institution to provide personnel training.

Site personnel will be trained on the process of data collection and delivery of the intervention prior to the enrollment of any patients. This training will be provided either by video/telephone conferencing or by on-site training. consist of either video training and telephone conferencing or on-site training. The content of the training will consist of co-developing or adapting site-specific standard operating procedures (SOPs) that accommodate local site environments while maintaining fidelity to the particular study arm to which sites have been randomized. Training will be provided by a member of the study team from Mayo Clinic.

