7.3 Site scheduling and clinic space requirements

Scheduling: Sites will need to determine the time needed to complete registration, pre-consultation decision aid interaction (for applicable study arms), and post-consultation questionnaire completion. Study coordinators will need to schedule patients to be present at the study site for sufficient time to complete pre- and post-consultation study items. Alternatively, sites must identify processes for pre- and post-consultation study requirements to be completed in very close proximity (1 business or less) to the visit.

Space requirements: Sites will need to identify and reserve an adequately private area near or adjacent to the patient waiting area. This space will be used to obtain patient consent for participation, obtain HIPAA authorization, and interact with the pre-consultation decision aid (for applicable study arms), and completion of the post-visit questionnaire.

Pre-consultation decision aid requirements: For study arms with the pre-consultation decision aid, this adjacent space must contain a computer terminal with internet access, or have wireless access provided to the room so that a tablet may be used.

During-consultation decision aid requirements: For study arms that will use the during-consultation decision aid, sites will need to ensure that exam rooms are provisioned with wireless internet access or contain a computer terminal with internet access. Either of these is needed in order for the physician to deliver the during-consultation decision aid.

Physician notification process: Sites should establish a local process for informing the participant's physician that the participant has completed pre-requisite study registration and intervention (where applicable). The physician will then be alerted to follow the during-consultation study procedures specific to his/her study site.

8.0**INTERVENTION**

While it is expected that registration will occur on the same day as the initial surgical consultation, the intervention (surgical consult visit) must occur within 14 days following registration. Registration may occur after the surgical consult visit and patient completion of the Baseline Questionnaire, but must be completed no later than the same day as the consultation.

Participating sites will be randomized to Pre- plus During-Consultation decision aids, Pre-consultation decision aid only, during-consultation only decision aid, or usual care arms.

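### The consultation clock in 8.2.4 follows only the physician although other staff may deliver Prostate Choice, so objective 2.2.5 can miss aid time; the stop event and the time endpoint also need a single definition

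*Combined protocol and SAP*

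**What the plan says.** Arm letters here follow section 8.0: A both aids, B Knowing Your Options only, C Prostate Choice only, D usual care.

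- **Objective (2.2.5).** "To compare clinic time required to administer the DA's across arms".
- **Clock (8.2.4, all arms).** "This will be defined as the time from when the physician enters the consultation room to when physician's consultative activities end". The end is then explained as "when the physician leaves the room OR when the patient is handed off to the CRA to complete post-consultation forms".
- **Who delivers the in-visit aid (8.2.4, Arm A; Arm C to the same effect).** "The physician or appropriate clinical staff (e.g., physician assistant) will incorporate the during-consultation decision aid in his/her conversation with the patient". In Arms A and B the physician or other clinical staff may also take the patient's questions about the pre-consultation aid.
- **Who delivers it according to 7.3.** In the room and equipment requirements only the physician is named: "Either of these is needed in order for the physician to deliver the during-consultation decision aid".
- **Pre-consultation aid time (8.2.4, Arms A and B).** "Site staff will record the time that the patient spends with the pre-consultation decision aid". Consultation time is kept apart: "The study coordinator will also assess the time for the consultation, which will be recorded in a separate field on the data collection forms".
- **Analysis (12.4.1 and 12.4.2).** Clinic time is a secondary endpoint, compared with a linear mixed model that has a fixed effect for each aid and a random site intercept. Neither section says which recorded time, or what sum, is the outcome.

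**The concern.** The objective concerns the time needed to administer the aids, but the clock is tied to one person who need not be the one administering Prostate Choice. Where delivery is delegated and happens outside the physician's presence, following the rule exactly leaves out the minutes that the objective is meant to measure.

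Two further gaps affect the same comparison. The stop is described by two events that need not coincide, with no rule on which prevails. The plan also does not say whether the separately recorded session with Knowing Your Options enters the endpoint, although that session is the main time cost of that aid.

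At stake is how the time result can be used. A clinic deciding whether to adopt an aid could read a small or null time effect as evidence of low burden when part of the burden was never on the clock. Unrecorded staff minutes and unknown stop events cannot be recovered afterwards.

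**Working it through.** The documents give no mean, standard deviation, expected difference or power for clinic time, so there is no stated figure to reproduce. The check compares the sections first and then uses illustrative arithmetic. Every duration and share below is an assumption.

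**1. Clock against delivery rule (both in 8.2.4).** The start is the physician's entry and the end is the end of the physician's activities. The deliverer may be the physician or other clinical staff.
- Physician delivers, or is present throughout: nothing is lost.
- Staff use the aid before the physician enters or after the physician leaves: that time is not counted.
- Staff run the whole visit: there is no start event.

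**2. Size of off-clock loss for Prostate Choice.** Let T be the true added minutes, s the share of visits with staff delivery, and f the share of aid time in those visits that falls outside the physician's clock. Measured addition = T × (1 − s × f). With T = 5:

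| s | f | Measured (min) | Loss (min) |
|---|---|---|---|
| 0 | any | 5.0 | 0 |
| 0.25 | 0.5 | 5 × 0.875 = 4.375 | 0.625 |
| 0.5 | 0.5 | 5 × 0.75 = 3.75 | 1.25 |
| 0.5 | 1 | 5 × 0.5 = 2.5 | 2.5 |
| 1 | 1 | 5 × 0 = 0 | 5.0 |

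The share lost is s × f whatever T is, so the loss is zero or downward. Applying this to the contrast between arms assumes that other off-clock staff contact is similar with and without the aid.

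**3. Stop event.** Section 12.2.2 expects 20 sites. Over four arms that is about five per arm, and each main effect compares about 10 sites with 10. Let g be the minutes between physician exit and hand-off, and q1 and q0 the shares of aid and no-aid sites using the later event. Shift in the contrast = g × (q1 − q0).
- q1 = q0: shift 0.
- q1 = 0.7, q0 = 0.3: +0.8 min at g = 2, +2.0 at g = 5, +4.0 at g = 10.
- q1 = 0.3, q0 = 0.7: the same values with a minus sign.

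If each site picked its event at random with probability 0.5, the added standard error is g × √(0.25 × (1/10 + 1/10)) = g × 0.224, which is 0.4 min at g = 2, 1.1 at g = 5 and 2.2 at g = 10. Because sites are randomized, a site's convention is nested within arm. The random intercept can carry the extra variance into the standard error but cannot remove a chance imbalance.

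**4. Which time is the endpoint.** Two times are recorded: consultation (all arms) and the session with the pre-consultation aid (Arms A and B). If only the first is modelled, the whole mean session is left out of the Knowing Your Options effect, whatever its length, and that aid can show a time effect only through the consultation. If the sum is modelled, the session is included. The text permits either.

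**The case against.** A fair defence has four parts.

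- **The protocol assumes a physician throughout.** Section 8.1 speaks of a first face-to-face visit with the doctor, 7.3 has the physician deliver the aid, and 8.2.5 follows a consultation with the physician. Section 8.2.3 notifies the physician or other clinical staff and then says that the physician will know what to do, so the word may be shorthand for the consulting clinician. In Arms A and C the aid is used inside the treatment conversation, not in a separate staff session. This makes off-clock delivery less likely, but it does not remove the explicit permission in 8.2.4 or its conflict with 7.3.
- **The stop rule has one governing criterion.** The end of the physician's activities controls, and the two events are ways of observing it. That is a reasonable reading. The hand-off can still come later than the exit, and the text does not say which one to record.
- **Site habits unrelated to arm are noise.** This stands. One deviant site among ten with a 10-minute gap moves a main-effect contrast by 10 × 1/10 = 1 minute, in either direction.
- **Pre-consultation aid time is already collected.** This stands too. That gap lies in the analysis plan. A total with zeros in Arms C and D makes that component of the Knowing Your Options effect positive by construction, so it must also be shown on its own.

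A reader might infer more: that the stop point does differ by site, and that 2.2.5 will understate the cost of both aids. The documents do not support this. No section assigns the stop event by site; 7.2 provides only for "co-developing or adapting site-specific standard operating procedures (SOPs) that accommodate local site environments", which makes variation plausible, and it also requires training on data collection. Understatement arises only if staff work outside the physician's presence, and the stop ambiguity can push the result either way.

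**Conclusion.** The point holds as a mismatch between a measurement rule and the delivery rule in the same section. The Prostate Choice time effect can be understated. The loss is the share s × f of the true added time, anywhere from none to all of it, and the documents give no basis for narrowing that range. The direction for the contrast rests on other off-clock staff contact being similar across arms.

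The two-event stop is a source of possible between-site noise without fixed direction. On assumed gaps of 2 to 10 minutes and random choice by site, it adds a standard error of about 0.4 to 2.2 minutes to a main effect. The missing endpoint definition would remove the main time cost of Knowing Your Options if only the consultation field were modelled; the text does not say that it will be.

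The change should be made because it is cheap and the lost minutes cannot be recovered. It concerns one secondary objective; the knowledge endpoint and the sample size are unaffected.

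**What to change.** **Section 8.2.4 and the form.** Time the consultation for whichever clinician, physician or other clinical staff, conducts any part of the consultation or the aid. Start at the first such clinician's entry and stop, in all arms and at all sites, when the last such clinician leaves. Note and subtract any interval with no clinician present; otherwise first-in to last-out timing would count idle waiting.

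**Sections 7.3 and 8.2.4.** Reconcile who may deliver the in-visit aid.

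**Sections 12.4.1 and 12.4.2.** Name the outcomes:
1. Clinician time by this clock, analysed with the existing mixed model.
2. Recorded on-site time with the pre-consultation aid, reported separately for Arms A and B.
3. Total on-site time, the sum of 1 and 2 with zero aid time in Arms C and D, analysed with the same model.

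**Cost.** Slightly more timing work for the coordinator, who must follow more than one clinician and note gaps; one extra model; and a flag on any data already timed under the present rule. No new visit is needed.

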8.2.5 Baseline Questionnaire

After consultation with the physician, the study coordinator will escort the patient to a private area preferably near to the patient waiting area, and provide the Baseline Questionnaire for the patient to complete before leaving.

8.3 12-month follow up

Follow up to ascertain the patient's overall and disease specific quality of life and prostate cancer treatment regret will be conducted by site coordinators 12 months (+/- 6 weeks) after the patient's consultation.

8.3.1 Twelve-month follow-up questionnaire

If the patient has a scheduled follow-up visit within this window, he should be asked to complete the 12-month Follow-up Questionnaire during this visit. If no visit is scheduled, site staff will mail the Follow-up Questionnaire with a self-addressed stamped envelope to the patient for him to complete at home and return to the clinic by mail. If the questionnaire is not returned by mail within 4 days, the study coordinator will call the patient (up to 5 attempts) to remind him to complete and mail the questionnaire or he or she will offer the patient the opportunity to complete the questionnaire over the phone.

8.3.2 Twelve-month follow-up chart review

At this time site staff will also conduct retrospective chart review to ascertain treatment utilization and complete the follow-up form. Treatment utilization will be categorized by the type of treatment the patient had (surgery vs. radiation vs. active surveillance).

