Prostate Choice is designed to cultivate better conversations about treatment risks and benefits contextualized in the unique features of the patient's disease and life circumstance. It will be used in tablet form as part of the clinical conversation in whatever way the patient and physician decide. Both will be briefed on its functionality by study personnel prior to the visit.

Knowing Your Options: a Decision Aid for Clinically Localized Prostate Cancer, is designed for pre-visit use. Knowing Your Options: A Decision Aid for Clinically Localized Prostate Cancer, was developed by the Agency for Healthcare Quality and Research (<http://www.effectivehealthcare.ahrq.gov/ehc/decisionaids/prostate-cancer>).⁶⁹ This non-proprietary web-based decision aid also uses the best available evidence and has been designed to be used in the out-of-visit/pre-visit setting. Similar to Prostate Choice, Knowing Your Options also allows for personalization for PCa severity in risk of cancer-specific mortality. It also queries patients about the

QOL issues regarding the different primary treatment options for PCa.^{69,70} To our knowledge its efficacy has not been formally tested. All other decision aids for PCa treatment are proprietary, or do not reflect the most recent evidence.

Knowing Your Options was designed as consumer information for patients searching the internet directly. It is one of two currently available tools online that seek to summarize research evidence for patients. Development details are available at <http://www.effectivehealthcare.ahrq.gov/ehc/decisionaids/prostate-cancer/>.

Knowing Your Options was designed to lay out the basic facts of treatment choices for patients prior to their appointment with their doctor with more extensive written explanation. In this trial, the Knowing Your Options tool will be administered prior to initial consultations with urologists when eligible patients are presenting to discuss treatment options in the days leading up to/on the day of that consultation.

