4.5 Stratification and Treatment Assignments

While not formal stratification factors, randomization will be set up so that sites will the particular capacities to oversample minority populations will be distributed between the arms, as illustrated in the diagram below.

Grouping Factors/Treatment assignments:

- Arm 1: Pre -and During Consultation Decision Aids
- Arm 2: Pre-Consultation Decision Aid only
- Arm 3: During Consultation Decision Aid only
- Arm 4: Usual Care

5.0**STUDY CALENDAR**

Laboratory and clinical parameters during treatment are to be followed using individual institutional guidelines and the best clinical judgment of the responsible physician. It is expected that patients on this study will be cared for by physicians experienced in the treatment and supportive care of patients on this trial.

Pre-Study Testing Intervals

- To be completed \leq 28 DAYS before registration: History and physical.
- To be completed \leq 90 DAYS before registration: PSA
- To be completed \leq 4 MONTHS before registration: Prostate Biopsy

	Prior to Registration	Baseline*	12 months after baseline**
Test and Observations			
History and Physical	X		
Height	X		
Weight	X		
Prostate biopsy	X		
Chart Review			X(1)
Labs and Staging			
PSA	X		
QOL Instruments			
Baseline Questionnaire		X(2)	
One-year Questionnaire			X(3)

* To be administered following the surgical consultation

** +/- 6 weeks

- 1 At 12 months site staff will review the patient's chart from the 6-month point to the 12-month time-point, collecting treatment information and any pertinent events.
- 2 Includes the Prostate Cancer Treatment Questionnaire and the Decisional Conflict Scale. See Section 10.0 and Appendix I.
- 3 Includes Expanded Prostate Cancer Index Composite (EPIC-26) and the Decisional Regret Scale. See Section 10.0 and Appendix II. To be completed by the patient during a clinic visit. If no clinic visit is scheduled +/- 6 weeks from the 12-month time-point, study staff should mail the 12-month questionnaire with a self-addressed stamped envelope to the patient for him to complete at home and return by mail (see Section 8.3.1).

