12.4 Supplementary Analysis Plans

12.4.1 Secondary endpoints

Secondary endpoints will be decisional quality, as measured by the DCS and Decisional Regret; clinical time required; patient QOL, which will be measured by questionnaires and converted into continuous summary scores using standard algorithms; and utilization, which will be categorized by the type of treatment the patient received, as determined by chart review at 12 months post-diagnosis. We will also consider the primary outcome of knowledge within only minority men (pooled) (defined as non-White or Hispanic White), as well as separately within the three racial subgroups. It is worth noting that some patients may receive a follow-up biopsy before these secondary endpoints are measured (at 12 months after first consultation), which could have a strong impact on their DCS and QOL scores. Thus, whether or not a patient receives a follow-up biopsy before 12 months (and the timing of this biopsy) will be taken into account when modeling these endpoints.

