APPENDIX I BASELINE QUESTIONNAIRE BOOKLET

Prostate Cancer Treatment Questionnaire

Please check the TRUE or FALSE box for each statement based on your knowledge of prostate cancer treatments. If you are not completely sure, mark 'Unsure'.

	True	False	Unsure
1. Most prostate cancer spreads quickly to other parts of the body	 1	 2	 3
2. Other illnesses can make treating prostate cancer more difficult	 1	 2	 3
3. Some treatments are better than others at stopping prostate cancer	 1	 2	 3
4. Radiation therapy from a machine for prostate cancer requires weeks of daily treatments	 1	 2	 3
5. Radiation seed therapy for prostate cancer requires weeks of daily treatments	 1	 2	 3
6. Radiation for prostate cancer can cause rectal pain	 1	 2	 3
7. Surgery for prostate cancer can cause urine leakage	 1	 2	 3
8. For most men, radiation therapy for prostate cancer has no effect on urinary control	 1	 2	 3
9. Both surgery and radiation can decrease sexual function	 1	 2	 3
10. Low-risk prostate cancer can be safely monitored	 1	 2	 3
11. After prostate cancer surgery, a man will go home with a catheter	 1	 2	 3
12. Hot flashes is a side-effect of hormone treatment	 1	 2	 3

Investigator developed.

Decisional Conflict Scale*My difficulty in making this choice***A. Which treatment option do you prefer? Please check one.**

- Surgery
- Radiation (includes Brachytherapy, IMRT, proton beam)
- Active Surveillance (also called watchful waiting)
- Unsure

B. Considering the option you preferred, please answer the following questions:

	Yes	Unsure	No

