--------------------------	--------------------------	--------------------------	--------------------------	--------------------------
- e. Change in body weight

				
--------------------------	--------------------------	--------------------------	--------------------------	--------------------------

Decisional Regret Scale

Please think about the decision you made about how to treat your prostate cancer after talking to your doctor. Please show how you feel about these statements by circling a number from 1 (strongly agree) to 5 (strongly disagree).

	Strongly Agree	Agree	Neither Agree nor Disagree	Disagree	Strongly Disagree
1. It was the right decision	1	2	3	4	5
2. I regret the choice that was made	1	2	3	4	5
3. I would go for the same choice if I had to do it over again	1	2	3	4	5
4. The choice did me a lot of harm	1	2	3	4	5
5. The decision was a wise one	1	2	3	4	5

Decision Regret Scale © AM O'Connor, 1996 University of Ottawa

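### Treatment utilization rests on chart review alone, and the 12-month booklet never asks which treatment the man received, so treatment given elsewhere may be missed or misclassified

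*Combined protocol and SAP*

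**What the plan says.** Treatment utilization is a secondary endpoint, named in objectives 2.2.1 to 2.2.3. On its source and coding the plan says:

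- Section 8.3.2: "At this time site staff will also conduct retrospective chart review to ascertain treatment utilization and complete the follow-up form".
- Section 12.4.1: utilization is the type of treatment received, "as determined by chart review at 12 months post-diagnosis".
- Section 8.3.2, categories: "Treatment utilization will be categorized by the type of treatment the patient had (surgery vs. radiation vs. active surveillance". No other category is named there.
- Section 5.0, Study Calendar, footnote 1: "At 12 months site staff will review the patient's chart from the 6-month point to the 12-month time-point, collecting treatment information".

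On what the man himself is asked:

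- Study Calendar, footnote 3, on the 12-month questionnaire: "Includes Expanded Prostate Cancer Index Composite (EPIC-26) and the Decisional Regret Scale".
- Appendix II, the lead-in to the regret items: "Please think about the decision you made about how to treat your prostate cancer after talking to your doctor". The items that follow ask how he feels about that decision, not what it was.
- Appendix I, in the booklet completed straight after the consultation: "Which treatment option do you prefer? Please check one". This records a preference, not a treatment received.

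**The concern.** Men enter the trial at their first consultation after diagnosis. Section 1.4 places the pre-visit aid "prior to initial consultations with urologists", and the Study Calendar calls the visit a surgical consultation. What follows, radiation in particular, need not happen at the same site. Section 13.1 requires a site to provide consultation; none of its listed criteria requires the site to treat or follow the man. Section 8.3.1 provides for men with no 12-month visit and reaches them by mail and then telephone, but only for a questionnaire that does not ask about treatment. These are the men whose site chart is most likely to be incomplete.

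A chart with no treatment in it resembles the chart of a man under surveillance. If treatment elsewhere is read that way, the surveillance share is overstated and the comparison between decision aids is distorted. Risk-concordant treatment is part of the study's stated aim (Section 1.2), so the surveillance share is a figure that readers will look at.

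**Working it through.** The plan states no rate, power or misclassification figure for utilization, so there is nothing of its own to reproduce. The check has two parts.

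**Reading the sections together.** Every statement on the source of utilization (Study Calendar footnote 1, Sections 8.3.2 and 12.4.1) names chart review and nothing else. No item in Appendix II asks which treatment was received, when or where. No text calls for outside records, a patient-reported cross-check, a code for treatment elsewhere or unknown, or positive evidence before surveillance is coded. In addition, footnote 1 confines the review to months 6 to 12, while Sections 8.3.2 and 12.4.1 seek treatment received by 12 months. Read literally, the footnote leaves out treatment in the first six months even when it was given on site.

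**Illustration under assumed inputs.** Let *a* be the true share under surveillance and *m* the share of treated men whose treatment is not in the chart. Neither is in the documents; *m* is varied from 0 to 30%. The only input from the plan is 172 patients, so 172 / 2 = 86 per side of each main effect.

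If missed men are coded as surveillance:

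coded share = a + (1 − a)m

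With equal *m* on both sides, the difference becomes (a₁ − a₀)(1 − m). Taking a₀ = 30% and a₁ = 50%:

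| m | coded a₀ | coded a₁ | difference | power, 86 vs 86 |
|---|---|---|---|---|
| 0 | 30% | 50% | 20 points | 77% |
| 10% | 30 + 70 × 0.10 = 37% | 50 + 50 × 0.10 = 55% | 18 | 66% |
| 20% | 30 + 70 × 0.20 = 44% | 50 + 50 × 0.20 = 60% | 16 | 56% |
| 30% | 30 + 70 × 0.30 = 51% | 50 + 50 × 0.30 = 65% | 14 | 46% |

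Power is two-sided at 0.05, at patient level with clustering ignored, so it is optimistic.

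With unequal *m* and no true effect (a = 30% on both sides), m = 10% against 30% gives 30 + 70 × 0.10 = 37% against 30 + 70 × 0.30 = 51%, a false difference of 14 points.

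If missed men are instead left missing and dropped:

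surveillance share among classified men = a / [1 − (1 − a)m]

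- Equal m = 20%, a = 30% and 50%: 0.30/0.86 = 34.9% and 0.50/0.90 = 55.6%. The difference stays near 20 points (20.7), but 86 × 0.70 × 0.20 = 12.0 and 86 × 0.50 × 0.20 = 8.6 men are lost.
- Unequal m, 10% against 30%, a = 30% on both sides: 0.30/0.93 = 32.3% and 0.30/0.79 = 38.0%, a false difference of 5.7 points.

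Whether a site treats its own patients is a site-level trait, and sites are the randomized unit. With about 20 sites, each main effect compares roughly 10 with 10, so capture can be unbalanced by chance. The random site intercept in Section 12.4.2 allows for between-site variation in the standard error. It does not restore the right category or correct the estimate.

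**The case against.** Four points can be made for the plan.

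1. The calendar speaks of the patient's chart, not of treatment delivered on site. Nothing excludes letters, referral notes or outside records held in it. This stands: absence from the chart is a risk, not a certainty.
2. The follow-up form that staff complete is not among the documents and may carry an other or unknown field. This also stands: coding such men as surveillance is nowhere stated as a rule.
3. No rate of outside treatment is given, so every percentage above is assumed. This is correct.
4. The endpoint is secondary. The sample size was set for knowledge, which is unaffected. This limits the priority but does not remove the point.

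A reader might go further and infer that the aids will move men from surgery on site to radiation elsewhere, and that the chart will report this as a move to surveillance, reversing the message. The documents do not support that. It needs every shifted man to leave the site, to leave no trace in its chart, and to be coded as surveillance. Section 1.4 says that Prostate Choice reviews all the options; it says nothing about where treatment is given. The literature table in Section 1.1 includes a trial in which fewer men chose surgery after an intervention (63% vs 85%), but that concerns the choice of treatment, not the place. Arm-dependent capture is possible; it is not shown.

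**Conclusion.** The point holds as a weakness in ascertainment. Chart review is the only named source, the 12-month booklet has no item on treatment received, and the plan's own site criteria and follow-up procedure make treatment elsewhere foreseeable. Men so treated may be coded as surveillance or left missing.

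The size cannot be computed. If they are coded as surveillance, equal under-capture shrinks true differences by the factor 1 − m, and unequal under-capture across sites can create false ones. If they are left missing, equal under-capture mainly costs numbers, and unequal under-capture still distorts, though less in the example above. Both readings rest on assumed rates and on a form that is not shown. The change is worth making because it is cheap and uses a contact already planned; it does not bear on the primary analysis.

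**What to change.** - **Appendix II booklet and its telephone version:** add one item asking which prostate cancer treatment or treatments the man has had, where, and in which month.
- **Sections 8.3.2 and 12.4.1:** define utilization from chart plus self-report. Use chart-documented treatment when present. If the chart shows none but the man reports one, classify by his report, checking outside records where they are readily available. Code active surveillance when the chart documents it or the man reports it and neither source records treatment. Otherwise code unknown.
- **Study Calendar footnote 1:** reconcile the month 6 to month 12 chart window with Sections 8.3.2 and 12.4.1.

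Surveillance should not require agreement between the two sources. That would leave a man with well-documented surveillance but no returned booklet without a code, and would concentrate missing data in that category.

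The cost is one extra question in a booklet already administered, a form field, and occasional record checks. Self-reported dates will be approximate.
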